9.5 ANTICIPATED ADVERSE EVENTS

Previous human experience and known adverse effects of the test product are detailed in the Product Information leaflet.

10 STATISTICAL METHODOLOGY

A total of 84 subjects, are expected to be recruited into study. The trial will follow-up eligible subject for a total duration of 12 months. One interim analysis is planned to be conducted at the time when approximately 50% of the subjects will reach Month 7 or early terminated the study.

10.1 INTERIM AND FINAL ANALYSES

One interim analysis is planned for possible early termination of the study.. The interim analysis will be performed at the time when approximately 50% of the subjects will reach Month 7 (1 month after the 3rd vaccine) or early terminated the study..

10.2 SIGNIFICANCE LEVEL

The overall significance level for this study will be 5% using two-tailed tests.

10.3 SAMPLE SIZE RATIONALE

Sample size determination was performed under the following assumptions:

- The primary endpoint for the study is the Seroprotection Rate (SPR), defined as the proportion of subjects with anti-HBs antibody titer at least equal to 10mIU/ml, at Month 7 (i.e. one month after the third immunization with Sci-B-Vac™). Subjects early terminated from the study for any reason at any time while having an anti-HBs antibody concentrations \geq 10mIU/ml will be considered among those who met endpoint.
- It is expected that the true rate of SPR following treatment with Sci-B-Vac™ is 95% or more.
- The principal analysis of the primary endpoint will be a non-inferiority analysis testing the below hypothesis:
 - ✓ $H_0: P-p_0 \leq -\text{Margin}$
 - ✓ $H_1: P-p_0 > -\text{Margin}$
- Where p_0 , the assumed true SPR is 95% and the non-inferiority margin is 9.0%, employing that study will be considered successful if the lower bound of the 95.0% exact CI will be 86.0% or more (lower non-inferiority limit).
- The rationale for sample size calculation is based on demonstrating an expected SPR rate of 95%. The lower bound of a calculated 95% confidence interval (CI) using Exact binomial method ensures that the actual SPR rate will not exceed the calculated lower limit (will not be lower than the lower bound).
- The sample size is adjusted to a total of 84 subjects to account for an anticipated withdrawal rate of approximately 20%.

	Protocol No.: SciB018
	Version and Date: Version 2.0, September 9, 2015 Amendment 1

Sample Size Justification:

When the sample size is 70, a one-sided 95.0% confidence interval (CI) for a single proportion using Exact binomial method will demonstrate a lower bound of 86.0% or more for an expected proportion of 0.95.

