10.3 SAMPLE SIZE RATIONALE

Sample size determination was performed under the following assumptions:

- The primary endpoint for the study is the Seroprotection Rate (SPR), defined as the proportion of subjects with anti-HBs antibody titer at least equal to 10mIU/ml, at Month 7 (i.e. one month after the third immunization with Sci-B-Vac™). Subjects early terminated from the study for any reason at any time while having an anti-HBs antibody concentrations \geq 10mIU/ml will be considered among those who met endpoint.
- It is expected that the true rate of SPR following treatment with Sci-B-Vac™ is 95% or more.
- The principal analysis of the primary endpoint will be a non-inferiority analysis testing the below hypothesis:
 - ✓ $H_0: P-p_0 \leq -\text{Margin}$
 - ✓ $H_1: P-p_0 > -\text{Margin}$

	Protocol No.: SciB018
	Version and Date: Version 1.0, March 4, 2015

- Where p_0 , the assumed true SPR is 95% and the non-inferiority margin is 12.5%, employing that study will be considered successful if the lower bound of the 95.86% exact CI (using the alpha level at final analysis) will be 82.5% or more (lower non-inferiority limit).
- Under these assumptions, sample of 70 subjects will provide a power of 86.1% or more to demonstrate that the observed SPR is non-inferior to the rate of 95%. Sample size is adjusted to a total of 84 subjects to account for an anticipated withdrawal rate of approximately 20%.

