5 SELECTION OF STUDY POPULATION

5.1 NUMBER OF SUBJECTS

Up to eighty four (84) healthy subjects will be enrolled in the study

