2.4 Study Populations

Up to ninety two (92) healthy subjects will be enrolled in the study

Intent-to-Treat (ITT) Population includes all enrolled subjects who were vaccinated at least once with Sci-B-Vac™. The Safety population will be same as ITT population.

Modified Intent-to-Treat (mITT) population is a subset of the ITT set. This set will consist of all enrolled subjects who were vaccinated at least once with Sci-B-Vac™ and had at least one post vaccination follow-up visit, fully comply with the study protocol, had no violation of any of the inclusion/exclusion criteria and did not demonstrate an anamnestic response after the 1st administration of Sci-B-Vac. An anamnestic response revealed by Sci-B-Vac is defined as anti-HBs level above 6000mIU/ml (the highest titer recorded upon Sci-B-Vac 1st injection) in a subject with no detectable anti-HBs antibody at visits 1 and 2. Subjects who early terminated the study but reached the primary endpoint will be included as well. Subjects who did not complete the full-course of vaccination (i.e. 3 injections) and did not reach SPR will be excluded from the mITT set. This analysis set will serve as the primary analysis set for efficacy and safety inference.

Full Treatment (FT) set is a subset of the mITT analysis set and will consist of all subjects who were vaccinated 3 times with Sci-B-Vac™ and had at least one visit following the 3rd vaccination.

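### Protocol v2.0 enrols 84 to keep 70 after about 20% withdrawal, but 84 covers only 16.7%; 20% leaves 67, and keeping 70 needs 88

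*Protocol*

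**What the plan says.** Protocol v2.0 section 10.3 builds the justification on 70 subjects: "When the sample size is 70, a one-sided 95.0% confidence interval (CI) for a single proportion using Exact binomial method" is said to give a lower bound of at least 86.0% when the expected proportion is 0.95. The same section then inflates: "The sample size is adjusted to a total of 84 subjects to account for an anticipated withdrawal rate of approximately 20" per cent. The synopsis repeats both statements. Section 5.1 sets the ceiling: "Up to eighty four (84) healthy subjects will be enrolled in the study".

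The success rule in section 10.3 reads "study will be considered successful if the lower bound of the 95.0% exact CI will be 86.0% or more (lower non-inferiority limit", where "the assumed true SPR is 95% and the non-inferiority margin is 9.0" per cent. Section 10.2 adds "The overall significance level for this study will be 5% using two-tailed tests". Version 2.0 states no power.

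The later SAP gives two other totals. Section 2.4 has "Up to ninety two (92) healthy subjects will be enrolled in the study". Section 2.6 ties 94 to the same withdrawal rate of about 20%, and then explains 92 as an enlargement to cover subjects excluded for an anamnestic response.

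**The concern.** A withdrawal rate applies to the subjects enrolled, so the required number is divided by one minus the rate. The protocol's total is what results from adding 20% to the required number, which is a smaller allowance. The plan therefore does not keep the 70 subjects on which its justification rests at the withdrawal rate it names.

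The number 70 also has a special position. With an exact binomial rule, the number of failures allowed rises in steps. Under the two-sided 95% interval, 70 is the smallest sample at which four failures still pass. A shortfall of three subjects could then cost one permitted failure as well as a little precision.

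**Working it through.** **Inputs.** Required n = 70, withdrawal about 20%, assumed true SPR 95% and limit 86.0% (95% less the 9.0-point margin), all from Protocol v2.0 section 10.3. Two-tailed 5% is from section 10.2. The one-sided wording is from the sizing sentence in section 10.3.

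**The plan's figure.** 70 × (1 + 0.20) = 84, an exact match.

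**The adjustment.**
- Remaining after 20% loss: 84 × 0.80 = 67.2, so 67.
- Enrolment needed to keep 70: 70 / 0.80 = 87.5, so 88.
- Withdrawal rate that 84 absorbs: 1 − 70/84 = 16.7%.
- The SAP's totals: 92 × 0.80 = 73.6, so 73; 94 × 0.80 = 75.2, so 75. 92 keeps 70 up to 1 − 70/92 = 23.9%.

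**The success rule.** With x successes in n, the exact lower limit is the a-quantile of Beta(x, n − x + 1), with a = 0.025 two-sided and a = 0.05 one-sided. The rule passes if this limit is at least 0.86. If f is the largest number of failures that passes, power is P(failures ≤ f) for a binomial with n subjects and failure probability 0.05.

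| Analysed n | Two-sided: max failures (limit; next) | Power | One-sided: max failures (limit; next) | Power |
|---|---|---|---|---|
| 67 | 3 (87.47%; 85.41%) | 56.7% | 4 (86.9%; 84.9%) | 75.7% |
| 70 | 4 (86.01%; 84.1%) | 72.8% | 4 (87.4%; 85.6%) | 72.8% |
| 73 | 4 (86.6%; 84.7%) | 69.9% | 5 (86.1%; 84.4%) | 84.2% |
| 84 | 5 (86.7%; 85.1%) | 75.7% | 6 (86.4%; 84.9%) | 87.3% |

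On the two-sided rule every n from 60 to 69 allows three failures; 57/60 passes with a lower limit of 86.08%.

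**Which sidedness fits the documents' figures.**
- The 86.0% quoted for n = 70 matches the two-sided limit for 66/70 (86.01%). The one-sided limit there is 87.4%.
- Protocol v1.0 section 10.3 states "sample of 70 subjects will provide a power of 86.1% or more", using a 95.86% interval and a limit of 82.5%. Read as two-sided (a = 0.0207), that rule allows five failures and gives 86.3%, close to the stated figure. Read as one-sided (a = 0.0414), it allows six and gives 94.0%.

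The figures therefore favour two-sided, although the sizing sentence says one-sided.

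**The case against.** The strongest objection accepts the arithmetic and disputes the consequence. A reader might infer that the slip leaves the trial with 56.7% power and room for only three failures. The documents do not support that without conditions.

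- **Sidedness.** On the one-sided wording, 67 and 70 both allow four failures and power is slightly higher at 67. SAP section 2.8 gives a further criterion, 95% of subjects observed to be seroprotected. That also shows no step: 64/67 is 95.5% and 63/67 is 94.0%; 67/70 is 95.7% and 66/70 is 94.3%; so three failures are allowed at either size.
- **Analysis set.** Protocol v2.0 section 10.4.1 keeps anyone vaccinated once who had a follow-up visit, and leavers at or above 10 mIU/ml count as successes. The number analysed could be anywhere from 67 to 84. The 75.7% at 84 is an upper figure: version 2.0 does not say how leavers below 10 mIU/ml are counted, and counting them as failures would lower it. SAP section 2.4 excludes leavers who did not complete three injections and did not reach seroprotection, so there some leavers are lost.
- **Discreteness.** On the two-sided rule, 70 is a local peak. Power is 64.7% at 60 and 63.9% at 79, so much of the drop from 70 to 67 reflects the steps of the exact test rather than three lost subjects.
- **Contingency.** Section 5.6 allows extra recruitment to be considered, with IRB approval, and the SAP's 92 removes the shortfall.

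All four points stand as limits on the consequence. None repairs the sentence in section 10.3. The word approximately does not rescue it, because 84 is exactly 70 × 1.2. The inflation makes sense only if withdrawals reduce the evaluable number, and on that premise it is miscalculated. The SAP does not correct it either, since it attributes 92 to anamnestic exclusions and gives 94 for withdrawal.

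**Conclusion.** The sizing statement in Protocol v2.0 section 10.3 and the synopsis is wrong. At 20% withdrawal, 84 enrolled leaves 67, three short of the 70 relied on; 84 covers 16.7%; 88 would be needed. This rests only on the document's own figures.

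The effect on power is a range. It is 56.7% at 67 against 72.8% at 70 if the two-sided 95% rule applies and every leaver is lost. There is no loss on the one-sided wording. If all 84 stay in the analysis, two-sided power is at most 75.7%. All of these assume a true SPR of 95%. The two-sided reading has the better support, but the protocol contradicts itself on it, so the loss of a permitted failure is conditional.

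The finding is limited to Protocol v2.0. At the SAP's 92, 73 remain after 20% withdrawal and the shortfall below 70 disappears. If anamnestic exclusions come on top, 92 leaves room for about three of them.

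**What to change.** Take one of two routes in Protocol v2.0 section 10.3 and the synopsis.

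1. **Keep 84.** State that it allows for a withdrawal rate of about 16.7%, and that 20% would leave 67. This costs one sentence in two places.
2. **Adopt the SAP's 92.** Align protocol sections 5.1 and 10.3, the opening of section 10, and the synopsis with it. State that 92 leaves 73 after 20% withdrawal (four failures allowed, power 69.9% on the two-sided rule). Correct the 94 in SAP section 2.6, which otherwise gives a second total for the same withdrawal rate. This needs no enrolment beyond what the SAP already plans.

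Enrolling 88 would also satisfy the arithmetic, but it leaves 70.4, with almost no room for one more withdrawal.

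On either route, reconcile the one-sided sizing sentence with the two-tailed level in section 10.2 first. Say also how leavers below 10 mIU/ml are counted. Then state the maximum number of failures for each evaluable n. On the two-sided rule that is three from 60 to 69 and four at 70.

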10.4 ANALYSES SETS

10.4.1 Modified Intent-to-Treat (mITT) Analysis Set

The Modified Intent-to-Treat (mITT) analysis set is a subset of the ITT set. This set will consist of all enrolled subjects who were vaccinated at least once with Sci-B-Vac™ and had at least one post study IP administration follow-up visit. This analysis set will serve as the primary analysis set for efficacy and safety inference.

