10.7.1 Primary Endpoint Definition and Analysis

The primary endpoint of the study is the Seroprotection rate (SPR), defined as the proportion of subjects with anti-HBs antibody titer at least equal to 10mIU/ml, at Month 7 (i.e. one month after the third immunization with Sci-B-Vac™). Subjects early terminated from the study for any reason at any time while having an anti-HBs antibody concentrations \geq 10mIU/ml will be considered among those who met endpoint.

	Protocol No.: SciB018
	Version and Date: Version 2.0, September 9, 2015 Amendment 1

The principal analysis of the primary endpoint will employ a non-inferiority analysis [SAS PROC FREQ with binomial (noninf margin=0.09 p=(1- α) exact)] statement will be used for testing the below hypothesis:

$$H_0: P-p_0 \leq -\text{Margin}$$

$$H_1: P-p_0 > -\text{Margin}$$

Where p_0 , the assumed true SPR is 95% and the non-inferiority margin is 9.0%, employing that study will be considered successful if the lower bound of the (1- α) exact CI will be 86.0% or more.

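### Protocol v2.0 sizes the trial as if leavers drop out of the analysis, its primary set keeps them, and the SAP keeps only the successful ones, so the sizing fits neither primary set

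*Protocol*

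**What the plan says.** **Sizing (Protocol v2.0, 10.3).** The size rests on 70 subjects: "When the sample size is 70, a one-sided 95.0% confidence interval (CI) for a single proportion using Exact binomial method will demonstrate a lower bound". The bound named there is at least 86.0%, at an expected proportion of 0.95. The assumed rate is "It is expected that the true rate of SPR following treatment with Sci-B-Vac™ is 95% or more". The hypothesis is set out as "the assumed true SPR is 95% and the non-inferiority margin is 9.0"%, and the "study will be considered successful if the lower bound of the 95.0% exact CI will be 86.0% or more (lower non-inferiority limit"). The move to 84 is explained by withdrawal: "The sample size is adjusted to a total of 84 subjects to account for an anticipated withdrawal rate of approximately 20"%.

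**Primary set (Protocol v2.0, 10.4.1 and 10.7).** Membership needs one dose and one later visit: "This set will consist of all enrolled subjects who were vaccinated at least once with Sci-B-Vac™ and had at least one post study IP administration". Section 10.7 uses this mITT set for the primary endpoint.

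**Scoring of leavers (Protocol v2.0, 10.7.1).** "Subjects early terminated from the study for any reason at any time while having an anti-HBs antibody concentrations" of 10 mIU/ml or more are counted as having met the endpoint. Nothing is written for leavers below 10 or without a titre, and there is no missing-data rule.

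**SAP.** Section 2.4 changes the set: "Subjects who did not complete the full-course of vaccination (i.e. 3 injections) and did not reach SPR will be excluded from the mITT set". Section 2.8 limits the final analysis to 12-month completers plus early terminators who had already met the endpoint. Enrolment becomes up to 92 (2.4; section 2.6 gives both 94 and 92). Section 2.6 repeats the justification based on 70 subjects.

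**The concern.** Adding subjects for withdrawal makes sense if those who withdraw leave the denominator. Under the protocol's mITT set most of them stay, so withdrawal lowers the analysed SPR instead of the analysed number. The population sized is 70 subjects at 95%. The population analysed is up to 84, some of them scored on a titre taken before the course was complete. Enrolling 88 instead of 84 would not cure this.

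The SAP does not restore the match. It removes incomplete-course leavers who failed and keeps those who succeeded, so the denominator depends on the outcome.

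The 86.0% rule decides whether a batch qualifies as the reference standard. If leavers count as failures, a batch that truly reaches 95% after the full course can fail because of withdrawal. If only failing leavers are removed, a batch at the limit passes more often than the stated error rate allows.

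**Working it through.** **Inputs.** From Protocol v2.0 10.3: 70 sized, 84 enrolled, about 20% withdrawal, true SPR 0.95, limit 86.0%. From SAP 2.4: up to 92 enrolled. Sidedness is inconsistent: 10.2 says 5% two-tailed, while the sizing sentence in 10.3 uses a one-sided 95% interval. Both are run. Leavers' SPR at exit, *q*, is not in the documents, so it is an assumption shown over a range.

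**1. The plan's own figures.** 70 × 1.2 = 84 reproduces the enrolment number (70 / 0.8 = 87.5, i.e. 88, does not). The exact lower bound for *x* of *n* is the *a* quantile of Beta(*x*, *n* − *x* + 1), with *a* = 0.025 (two-sided) or 0.05 (one-sided). The expected count is 0.95 × 70 = 66.5. For 66/70 the bound is 86.01% two-sided and 87.4% one-sided; for 67/70 it is 88.0% and 89.3%. The statement in 10.3 reproduces. At either level 66/70 is the smallest passing count, so the chance of success is P(Bin(70, 0.95) ≥ 66) = 72.8%. Protocol v2.0 states no power; this figure is used here as the benchmark.

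**2. Protocol v2.0 mITT set.** With 84 analysed, success needs 79/84 (two-sided, at most 5 failures) or 78/84 (one-sided, at most 6). Take 20% of 84 ≈ 17 leavers before Month 7 and 67 completers at 95%, with leavers below 10 mIU/ml scored as failures. Completers alone are expected to give 67 × 0.05 = 3.35 failures; at *q* = 80% leavers add 17 × 0.20 = 3.4. The chance of success is P(Bin(67, 0.95) + Bin(17, *q*) ≥ 79 or 78):

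| Leavers' exit SPR *q* | Two-sided (79/84) | One-sided (78/84) |
|---|---|---|
| 95% | 75.7% | 87.3% |
| 90% | 60.7% | 76.0% |
| 80% | 31.8% | 48.0% |
| 70% | 12.4% | 23.2% |
| 50% | 0.7% | 2.0% |

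The benchmark of 72.8% is reached at *q* of about 94% (two-sided) or 89% (one-sided). Success and failure are equally likely at about 86.5% or 81%.

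**3. Fewer leavers before Month 7.** With 8 instead of 17, the chance at *q* = 80% is 54.3% (two-sided) or 70.7% (one-sided), and at *q* = 50% it is 16.5% or 30.1%.

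**4. SAP set.** Of 92 enrolled, 20% is about 18 leavers, leaving 74 completers. If *k* leavers are kept, all as successes, then *n* = 74 + *k* and the completers must supply the required count minus *k*.

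- Completers at 95%. With *k* = 0 the requirement is 70/74 or 69/74: 68.9% two-sided, 83.5% one-sided. With *k* = 9 it is 78/83 or 77/83, i.e. 69 or 68 of 74 completers: 83.5% and 92.3%. There is no collapse.
- Completers at a true 86%, two-sided rule. With *k* = 0, P(Bin(74, 0.86) ≥ 70) = 1.7%. With *k* = 9 only 69 of 74 completers are needed: 4.3%. Averaging over *k* ~ Bin(18, *s*), where *s* is the share of leavers who are seroprotected and kept, gives about 4% at *s* = 50% and about 6% at *s* = 80%, against a nominal 2.5%.

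**The case against.** A reader might infer that the protocol's trial is bound to be underpowered, or that a truly adequate batch will more likely fail than pass. The documents do not support that.

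- The loss depends on an exit SPR that they do not give. At 90% the one-sided rule still gives 76.0%, above the benchmark.
- The 20% refers to a study with 12 months of follow-up. Those who leave after Month 7 already have their Month 7 result, and those with no follow-up visit are outside the mITT set, so 17 affected leavers is an upper case.
- Scoring leavers below 10 mIU/ml as failures is the natural reading of a proportion of subjects meeting the endpoint, but it is not written.

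Section 10.3 can also be read as expecting 95% for the endpoint with its early-terminator rule already included. In that case 84 subjects give 75.7% or 87.3% and nothing is lost. But then subjects kept in the denominator need no allowance for withdrawal, and the stated reason for 84 falls away.

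A reader might also carry the loss over to the SAP. That would be wrong: SAP 2.4 and 2.8 remove the very leavers who cause it, and enrolment rises to 92. The SAP's version history mentions protocol changes, so a protocol later than v2.0 may exist; the figures for the protocol set apply to v2.0 only.

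Finally, the FT set (Protocol 10.4.2) is already reported for the primary endpoint (Protocol 10.8, SAP Table 14.2-2), and Protocol 5.6 allows further recruitment. Both help, but 10.8 promises only descriptive statistics for FT, and recruitment does not change how leavers are scored.

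These points limit the size and scope of the concern. They do not remove the mismatch between the sizing and either primary set.

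**Conclusion.** The point holds in a conditional form. Protocol v2.0 sizes for a population without leavers and analyses one that keeps most of them. If 17 leave before Month 7 and those below 10 mIU/ml count as failures, the chance of success drops from 72.8% to 32% (two-sided) or 48% (one-sided) at an exit SPR of 80%. It does not fall below the benchmark when exit SPR is at least about 94% or 89%. With 8 such leavers at 80% it is 54% or 71%, so under the one-sided bound the loss is then slight.

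Under the SAP the error runs the other way. Keeping only successful incomplete-course leavers raises the chance that a batch at 86% passes the two-sided rule from 1.7% to about 4% to 6%, against a nominal 2.5%. This assumes 74 completers, 18 leavers, and 50% to 80% of leavers seroprotected and kept; it ignores the SAP's other exclusions.

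The two documents define the primary set differently, and the sizing statement describes neither.

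**What to change.** 1. Reconcile the Protocol and SAP mITT definitions into one primary set whose membership does not depend on whether the subject reached the titre endpoint.
2. State how leavers below 10 mIU/ml, and leavers without a titre, are scored.
3. State whether the 95% exact bound is one-sided or two-sided, and use the same bound in the sizing and in the success rule.
4. Restate Protocol 10.3 and SAP 2.6 for that set, each with its own enrolment number, giving the required count and the chance of success over a stated range of exit SPR. For 84 analysed, the table above can serve. The SAP needs figures for its own number, not 79/84.
5. Apply the exact interval and the 86.0% rule to the FT set (three doses plus a later visit) as a supporting analysis, since it is closest to the population that was sized.

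Cost: wording in both documents and one table. No extra subjects are needed. The stated chance of success will look less favourable.
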